### **3.2 Secondary Endpoints**

**3.2.1** Changes in other objective (HVLT-R, RVP, OTS, Digit Span, COWA, Animal Naming Test) and self-reported (PROMIS Cognitive Function) cognitive measures will be measured from pre- to post-chemotherapy.

**3.2.2** Depression (PROMIS-Depression), Anxiety (PROMIS-Anxiety), fatigue (Functional Assessment of Chronic Illness Therapy – Fatigue, FACIT-F), menopausal status (Hormonal Status Questionnaire and follicle stimulating hormone level, FSH), and perceived cognitive effort (NASA-Task Load Index, NASA-TLX) will be measured pre- and post-chemotherapy. Baseline IQ (Wechsler Adult Test of Reading, WTAR) will be measured pre-chemotherapy only.

**3.2.3** Health-related quality of life (Functional Assessment of Cancer Therapy – General, FACT-G) and functional status (Patient-reported Karnofsky Performance Status, Patient-KPS) will be measured pre- and post-chemotherapy.

**3.2.4** Recruitment will be measured as proportion of approached participants who agree to enroll and number of participants enrolled per month. Retention will be measured as proportion of enrolled participants who complete the primary outcome measure pre- and post-chemotherapy. Adherence will be measured as patient-reported proportion of prescribed doses of memantine actually taken.

**3.2.5** Safety will be measured as the frequency of reported adverse events (AEs).

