#### 5.2 Treatment Dosage and Administration

Participants will receive memantine beginning within four weeks prior to and one week after chemotherapy initiation. All patients will be gradually titrated to 10 mg twice daily as follows: 5 mg daily in week 1, 5 mg twice daily in week 2, 5 mg each morning and 10 mg each evening in week 3, then 10 mg twice daily in week 4. Participants will continue 10 mg twice daily until 4 weeks (range: 2 to 12

weeks) after the last dose of chemotherapy. Depending on the chemotherapy regimen, total duration will range from approximately 12-30 weeks.

| REGIMEN DESCRIPTION |       |                                       |                                     |
|---------------------|-------|---------------------------------------|-------------------------------------|
| Agent               | Route | Dose                                  | Schedule                            |
| Memantine HCl       | Oral  | 5 mg daily                            | Week 1                              |
|                     |       | 5 mg twice daily                      | Week 2                              |
|                     |       | 5 mg each morning, 10 mg each evening | Week 3                              |
|                     |       | 10 mg twice daily                     | Week 4 to 4 weeks post-chemotherapy |

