### 5.3 Toxicities and Dosing Delays

Any patient who receives treatment on this protocol will be evaluated by the CRA, PI, or Co-Is for toxicity. Patients will be assessed at least weekly during the titration of memantine and no less frequent than every three weeks during systemic chemotherapy. For patients receiving anti-HER2 directed therapy in addition to chemotherapy, toxicity will only be assessed during the chemotherapy segment of the regimen.

Toxicity will be assessed according to the NCI Common Toxicity Criteria for Adverse Events (CTCAE), version 5.0.

In assessing adverse events (AEs) and attribution during the course of this study, we will consider those AEs commonly associated with memantine, the specific chemotherapy administered, and chemotherapy-associated medications received.

Though all patient-reported symptoms will be recorded and examined for their association with memantine, the following most common side effects of memantine will be explicitly solicited from participants by the study team: headache, dizziness, confusion, constipation, diarrhea, and fatigue. See section 6.1.7 for additional information on memantine warnings and precautions. Differentiation between memantine-associated toxicities and toxicities attributable to alternative agents will be guided by Assessing of Causality of Adverse Events outlined in 8.1.2. The treating provider will be notified of any possible, probable, or definite AEs and involved in decisions to continue, dose reduce, or stop memantine. At any time, the participant may decide to dose reduce or discontinue memantine.

If a participant experiences a grade 1 toxicity with a probable or definite attribution to memantine, the participant will remain on the same dose and symptoms will be monitored daily until the side effect is resolved.

If a participant experiences a grade 2 toxicity with a probable or definite attribution to memantine, the dose will be reduced to 5 mg PO BID (or the last tolerated dose if less) and symptoms will be monitored daily until the side effect is resolved. If no improvement, memantine will be discontinued.

If a participant experiences a grade 3 toxicity with a probable or definite attribution to memantine, the participant will discontinue memantine.

If a participant experiences toxicity with a possible attribution to memantine, the participant will remain on the same dose of memantine and symptoms will be monitored weekly until the side effect is resolved.

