#### **7.10 Assessment of Safety**

Any patient who receives at least one dose of study therapy on this protocol will be evaluable for toxicity. Each patient will be assessed at least weekly during the titration of memantine and no less frequent than every three weeks during systemic chemotherapy for the development of any toxicity according to the Time and Events table. Toxicity will be assessed according to the NCI CTCAE version 5.

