### 9.3 Data Analysis Plans

The primary outcome is change in the DMS score. A paired t-test will test if the change in DMS score from pre- to post-chemotherapy is statistically different from historical controls. Pre- to post-chemotherapy, as well as pre- to 6 months post-chemotherapy, changes in all other cognitive measures will also be evaluated using paired t-tests.

Linear regression models will be used to cross-sectionally evaluate associations between depression (PROMIS-D), anxiety (PROMIS-A), sleep (PROMIS-Sleep Disturbance), menopausal status, fatigue (FACIT-F), estimated pre-cancer IQ (WTAR), and cognitive effort (NASA-TLX) with both objective (DMS, HVLT-R, COWA, ANT, Digit Span) and self-reported (PROMIS) measures of cognitive function at baseline and post-chemotherapy. Linear mixed effects models will evaluate associations across pre- and post- time points.

Linear regression modeling will describe the associations between pre- to post-chemotherapy cognitive changes (DMS, HVLT-R, COWA, ANT, Digit Span, PROMIS) with post-chemotherapy depression and anxiety (PROMIS), HRQOL (FACT-G), and performance status (KPS).

Descriptive statistics will be used to estimate feasibility: 1.) recruitment rate (% of invited participants who enroll), 2.) attrition (% of enrolled participants who are not eligible for analysis of the primary outcome), and 3.) adherence to treatment (% self-reported doses of memantine taken).

We will tabulate all AEs, the dose at which they occurred, and if they led to dosing delays or removal from the study.

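### The by-dose adverse event table in Section 9.3 states no exposure at each dose, so its counts would mainly track time at dose

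*Combined protocol and SAP*

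**What the plan says.** The AE analysis in Section 9.3 is one sentence, which begins "We will tabulate all AEs, the dose at which they occurred". Its remaining clause adds whether an event caused a delay or a removal. Section 7.10 supplies the only safety denominator: "Any patient who receives at least one dose of study therapy on this protocol will be evaluable for toxicity". That set is not divided by dose or by time, and no section gives participants or patient-weeks at each dose.

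The titration schedule in Section 5.2 is "5 mg daily in week 1, 5 mg twice daily in week 2, 5 mg each morning and 10 mg each evening in week 3". The target dose applies from week 4 onward, for a total of about 12 to 30 weeks. Memantine may start from four weeks before to one week after the first chemotherapy dose.

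Section 5.3 sets the contacts: "Patients will be assessed at least weekly during the titration of memantine and no less frequent than every three weeks during systemic chemotherapy". It also names 5 mg twice daily as the reduced dose after certain toxicities, which is the same dose as the week 2 step. Section 8.2 collects AEs from day 1 until 30 days after treatment stops, with onset date, grade and relationship to study drug.

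**The concern.** The plan classifies AEs by dose, and participants spend very different lengths of time at each dose. Without exposure beside the counts, the target dose will usually show most of the events whether or not dose matters. A real excess in a one-week titration step could be lost beside 9 to 27 weeks at the target dose.

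Four features of the design add to the difficulty:

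- **Contact frequency.** Contacts are closer together in titration than later.
- **Mixed dose level.** The 5 mg twice daily level combines people on their way up with people reduced because of toxicity or low creatinine clearance.
- **Chemotherapy timing.** Titration may be over before chemotherapy starts or may fall within the first cycles.
- **Off-drug events.** Events in the 30 days after stopping have no stated dose column.

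What is at stake is secondary objective 2.2.5, the description of safety, and its use in planning the larger placebo-controlled study mentioned in Section 9.2.

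**Working it through.** **Inputs**

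- Weeks below the target dose: 3 (Section 5.2).
- Total duration: T = about 12 to 30 weeks (Section 5.2).
- Start window: 4 weeks before to 1 week after the first chemotherapy dose (Section 5.2).
- End: 4 weeks (range 2 to 12) after the last chemotherapy dose (Sections 5.2 and 5.5).
- Last chemotherapy dose, counted from the first, by regimen (Section 5.1): TC week 9; TCH week 15; AC-T week 8 + 11 = 19. The AC-T figure assumes weekly taxol.

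**Reproducing the plan's duration**

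T = weeks on memantine before chemotherapy + week of last chemotherapy dose + weeks after it.

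- TC, start 1 week after, end 4 weeks after: -1 + 9 + 4 = 12 weeks.
- AC-T, start 1 week after, end 12 weeks after: -1 + 19 + 12 = 30 weeks.

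The stated 12 to 30 weeks is reproduced. The full windows run wider, from -1 + 9 + 2 = 10 weeks (TC) to 4 + 19 + 12 = 35 weeks (AC-T).

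**Expected share of events at the target dose with no dose effect**

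Base case: constant weekly rate, equal ascertainment, no reductions or early stops, on-treatment events only. Share = (T - 3)/T.

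- T = 12: 9/12 = 75%.
- T = 30: 27/30 = 90%.

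Each titration step lasts one week, so the target dose would hold 9 to 27 times the count of any single step.

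**Changing one assumption at a time.** The 20%, 50% and two-fold values are assumptions, not figures from the documents.

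| Change | Short course | Long course |
|---|---|---|
| Full windows, T = 10 and 35 | 7/10 = 70% | 32/35 = 91% |
| Exposure and counting end at the last chemotherapy dose (one reading of Section 6.1.4), 8 and 23 weeks | 5/8 = 62.5% | 20/23 = 87% |
| 20% of participants reduced after week 6, T = 12 and 30 | (0.8×9 + 0.2×3)/12 = 65% | (0.8×27 + 0.2×3)/30 = 74% |
| 20% stopped after week 6 | 7.8/(0.8×12 + 0.2×6) = 72% | 22.2/(0.8×30 + 0.2×6) = 88% |
| 30-day off-drug window (30/7 weeks) added to the total | 9/16.29 = 55% | 27/34.29 = 79% |
| Titration contacts capture twice as many events | 9/(9 + 6) = 60% | 27/(27 + 6) = 82% |
| 50% reduced after week 4 | (0.5×9 + 0.5×1)/12 = 42% | (0.5×27 + 0.5×1)/30 = 47% |
| 50% reduced after week 6 | (0.5×9 + 0.5×3)/12 = 50% | (0.5×27 + 0.5×3)/30 = 50% |

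The target dose keeps the majority unless about half of participants reduce early.

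**Masking.** Suppose the week 1 rate were three times the later rate. Week 1 would then contribute 3 units of events against 9 to 27 at the target dose, so the raw counts would still point to the target dose.

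**With exposure shown.** At a constant rate r, the target dose gives (T - 3)r/(T - 3) = r and each step gives 1r/1 = r. The rate ratio is 1.0, as it should be.

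**Precision.** With 56 participants, each one-week step has at most 56 × 1 = 56 patient-weeks.

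**The case against.** The sentence in Section 9.3 can be read as recording three attributes of each AE: dose, delay and removal. It does not announce a comparison across doses. The objective is only to describe safety, no dose-response test is planned, and a denominator is not ruled out. This is a fair reading and it limits the severity. It does not remove the point, because a table that classifies events by dose invites that comparison and nothing in the plan supplies the exposure needed to make it.

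A reader might also infer more than the documents support:

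- **That 75% to 90% is a forecast.** It is an expected share under the base-case assumptions. The plan itself departs from several of them: Section 5.3 provides for reductions and stops, contact intervals differ, and Section 8.2 includes off-drug events.
- **That Section 3.2.5 counts events rather than participants.** It speaks of frequency, a word that Section 6.1.7 uses for percentages, and Section 7.10 defines a participant denominator. The wording does not settle the matter.
- **That overlap with chemotherapy toxicity is ignored.** Section 8.1.2 grades causality on worsening in severity or frequency as well as on presence, and Section 8.2 records relationship for each event.
- **That contacts are exactly weekly and then exactly three-weekly.** These are minimum frequencies, and Section 5.3 adds daily or weekly monitoring after some toxicities.
- **That everything needed is already recorded.** AE onset dates are, and dose at onset must be known to build the planned table. But the Time and Events Table in Section 7.1 lists no dosing log, and Section 7.3 tracks adherence by participants' estimates of missed doses.

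**Conclusion.** The concern holds in a limited form. As written, the by-dose table would mainly reflect time at dose. In the base case 75% to 90% of events fall at the target dose with no dose effect. Most of the alternatives tried give about 55% to 90%, and 42% to 50% results only if half of participants reduce early. The table therefore cannot support a statement about dose, and it could mask a titration-phase signal. It drives no dosing decision and no test, and the primary DMS analysis does not depend on it. This is a low-severity improvement to a descriptive table, not an error that alters the trial's main conclusion.

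**What to change.** In Section 9.3:

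1. Report participants with at least one event, by worst grade and attribution, among those who received at least one dose.
2. In the by-dose table, show participants and patient-weeks at each dose, with events per patient-week.
3. Show 5 mg twice daily as a titration step separately from 5 mg twice daily as a reduced dose, and show events in the 30-day off-drug window separately.
4. Note beside the table that contacts are at least weekly in titration and at least every three weeks afterwards.
5. Limit any split by chemotherapy phase to an overall summary. With 56 participants, a split for every AE term would leave many cells nearly empty.

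Two things are needed first. Confirm that dose-change dates are captured. Reconcile the end of target dosing, which Sections 5.2 and 5.5 place after the last chemotherapy dose and Section 6.1.4 places at the end of chemotherapy, because person-time is undefined until they agree.

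The cost is a slightly longer table and the work of deriving patient-weeks from dose-change dates, with some added data capture if those dates are not now recorded. Rates for the one-week steps will be imprecise, at no more than about 56 patient-weeks each, and should be presented as such.

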## 10.0 STUDY MANAGEMENT

### 10.1 Institutional Review Board (IRB) Approval and Consent

It is expected that the IRB will have the proper representation and function in accordance with federally mandated regulations. The IRB should approve the consent form and protocol.

In obtaining and documenting informed consent, the investigator should comply with the applicable regulatory requirement(s), and should adhere to Good Clinical Practice (GCP) and to ethical principles that have their origin in the Declaration of Helsinki.

Before recruitment and enrollment onto this study, the patient will be given a full explanation of the study and will be given the opportunity to review the consent form. Each consent form must include all the relevant elements currently required by the FDA Regulations and local or state regulations. Once this essential information has been provided to the patient and the investigator is assured that the patient understands the implications of participating in the study, the patient will be asked to give consent to participate in the study by signing an IRB-approved consent form.

Prior to a patient's participation in the trial, the written informed consent form should be signed and personally dated by the patient and by the person who conducted the informed consent discussion.

### 10.2 Required Documentation

Before the study can be initiated at any site, the following documentation must be provided to the Clinical Protocol Office (CPO) at the University of North Carolina.

- A copy of the official IRB approval letter for the protocol and informed consent
- CVs and medical licensure for the principal investigator and any associate investigators who will be involved in the study
- A copy of the IRB-approved consent form

### 10.3 Registration Procedures

Patient enrollment in the study will be tracked in OnCore®. This will allow the UNC Lineberger Comprehensive Cancer Center to track accrual into the study. For all potentially eligible and interested patients, eligibility criteria must be confirmed prior to registration by the PI.

## 10.4 Adherence to the Protocol

Except for an emergency situation in which proper care for the protection, safety, and well-being of the study patient requires alternative treatment, the study shall be conducted exactly as described in the approved protocol.

### 10.4.1 Emergency Modifications

UNC investigators may implement a deviation from, or a change of, the protocol to eliminate an immediate hazard(s) to trial participants without prior UNC IRB approval.

For any such emergency modification implemented, a UNC IRB modification form must be completed by UNC Research Personnel within five (5) business days of making the change.

### 10.4.2 Single Patient/Participant Exceptions

Any request to enroll a single participant who does not meet all the eligibility criteria of this study requires the approval of the UNC Principal Investigator and the UNC IRB.

### 10.4.3 Other Protocol Deviations/Violations

According to UNC's IRB, a protocol deviation is any unplanned variance from an IRB approved protocol that:

- Is generally noted or recognized after it occurs
- Has no substantive effect on the risks to research participants
- Has no substantive effect on the scientific integrity of the research plan or the value of the data collected
- Did not result from willful or knowing misconduct on the part of the investigator(s).

An unplanned protocol variance is considered a violation if the variance meets any of the following criteria:

- Has harmed or increased the risk of harm to one or more research participants.
- Has damaged the scientific integrity of the data collected for the study.
- Results from willful or knowing misconduct on the part of the investigator(s).
- Demonstrates serious or continuing noncompliance with federal regulations, State laws, or University policies.

If a deviation or violation occurs please follow the guidelines below:

**Protocol Deviations:** UNC or Affiliate personnel will record the deviation in OnCore®, and report to any sponsor or data and safety monitoring committee in accordance with their policies. Deviations should be summarized and reported to the IRB at the time of continuing review.

**Protocol Violations:** Violations should be reported by UNC personnel within one (1) week of the investigator becoming aware of the event using the same IRB online mechanism used to report Unanticipated Problems.

**Unanticipated Problems:** Any events that meet the criteria for “Unanticipated Problems” as defined by UNC’s IRB must be reported by the study personnel using the IRB’s web-based reporting system.

#### **10.5 Amendments to the Protocol**

Should amendments to the protocol be required, the amendments will be originated and documented by the Principal Investigator at UNC. It should also be noted that when an amendment to the protocol substantially alters the study design or the potential risk to the patient, a revised consent form might be required.

The written amendment, and if required the amended consent form, must be sent to UNC’s IRB for approval prior to implementation.

#### **10.6 Record Retention**

Study documentation includes all eCRFs, data correction forms or queries, source documents, Sponsor correspondence to Investigators, monitoring logs/letters, and regulatory documents (e.g., protocol and amendments, IRB correspondence and approval, signed patient consent forms).

Source documents include all recordings of observations or notations of clinical activities and all reports and records necessary for the evaluation and reconstruction of the clinical research study.

Government agency regulations and directives require that all study documentation pertaining to the conduct of a clinical trial must be retained by the study investigator. In the case of a study with a drug seeking regulatory approval and marketing, these documents shall be retained for at least two years after the last approval of marketing application in an International Conference on Harmonization (ICH) region. In all other cases, study documents should be kept on file until three years after the completion and final study report of this investigational study.

#### **10.7 Obligations of Investigators**

The Principal Investigator is responsible for the conduct of the clinical trial at the site in accordance with Title 21 of the Code of Federal Regulations and/or the Declaration of Helsinki. The Principal Investigator is responsible for personally overseeing the treatment of all study patients. The Principal Investigator must assure that all study site personnel, including sub-investigators and other study

staff members, adhere to the study protocol and all FDA/GCP/NCI regulations and guidelines regarding clinical trials both during and after study completion.

The Principal Investigator will be responsible for assuring that all the required data will be collected and entered into the eCRFs. Periodically, monitoring visits will be conducted and the Principal Investigator will provide access to his/her original records to permit verification of proper entry of data. At the completion of the study, all eCRFs will be reviewed by the Principal Investigator and will require his/her final signature to verify the accuracy of the data.

## 12.0 APPENDICES

### Appendix A: Delayed Matching to Sample Test (DMS)

[figure not shown]
The participant is shown a complex visual image.

The image is hidden from the participant, and the participant is shown four similar images simultaneously or after a 4- or 12-second delay.

The participant must select the image that exactly matches the sample.

## Appendix B: Rapid Visual Information Processing (RVP)

The participant is asked to recognize a target digit sequence out of a series of pseudo-random digits from 2 to 9.

[figure not shown]
The participant presses a button on the bottom of the screen as quickly as possible after they recognize the target digit sequence.

[figure not shown]

[figure not shown]
